8. SAFETY ANALYSES

The safety analyses will be based on the Safety population. Unless otherwise specified data reported as part of the no-treatment follow-up will not be included in summaries of on-treatment data or post-treatment data. Data reported during the no-treatment follow-up will be summarised separately.

Summaries of adverse events (AEs), serious adverse events (SAEs) and other significant AEs will be based on GSK Core Data Standards. The details of the planned displays are provided in [Appendix 12: List of Data Displays](#).

8.1. Adverse Events Analyses

8.2. Adverse Events of Special Interest Analyses

Adverse events of special interest (AESIs) are adverse events which are to be closely monitored as the development of mepolizumab progresses.

Systemic reactions are AESIs which are collected via targeted eCRF and further categorised by the investigator as either an allergic (type I hypersensitivity) or other systemic reaction. These events are required to be assessed against Sampson's diagnostic criteria for anaphylaxis. Local injection site reactions are also collected via targeted eCRF within the study.

AESIs of potential opportunistic infections, malignancies, serious cardiac, vascular and thromboembolic (CVT) events and serious ischemic events will be identified from a list

of relevant preferred terms maintained within a project level reference dataset created based on the MedDRA dictionary available at the time of source data lock for this study. Further details of how relevant preferred terms are identified for the AESIs are given in the Program Safety Analysis Plan (PSAP).

Separate summary tables showing the number and percent of participants with each type of AESI, broken down by preferred term will be created. These summaries will be reported as part of the standard AE/SAE tables for the AESIs of infections, serious infections, neoplasms, cardiac disorders and serious cardiac disorders. The relative risk of each AESI between mepolizumab and placebo will be presented with 95% confidence intervals.

For each AESI a profile summary table will be produced containing information on event characteristics including, but not be limited to, the number of participants with the AESI, the number of occurrences of the AESI, the number of participants with a serious event or a drug related event, summaries by maximum severity and separately by outcome.

Separate listings will be provided of participants with systemic reactions identified by the investigator as meeting the criteria for anaphylaxis, systemic reactions categorised as allergic (type I hypersensitivity), systemic reactions categorised as other, and all other AESIs.

8.3. Clinical Laboratory Analyses

Summaries of laboratory data including chemistry and haematology parameters, and liver function test data will be based on GSK Core Data Standards and unless otherwise specified will include on-treatment and post-treatment data.

A scatter plot of maximum post-baseline ALT vs maximum post-baseline total bilirubin will be produced. In addition, if any liver stopping or liver monitoring events occur during the study, summaries of liver monitoring/stopping event reporting and hepatobiliary laboratory abnormalities will be produced.

The details of the planned displays are in [Appendix 12: List of Data Displays](#).

8.4. Other Safety Analyses

8.4.1. ECG and Vital Signs

Summaries of ECG and vital signs data will be based on GSK Core Data Standards. The details of the planned displays are presented in [Appendix 12: List of Data Displays](#).

For ECG data, summaries of the maximum post-baseline and change from baseline values for QTc(F), QTc(B) and heart rate will be provided.

Individual maximum and maximum change from baseline QTc(F) and QTc(B) values will be categorised as detailed in Section 14.6.6. The number (percent) of participants in each of the categories will be displayed.

The number of abnormal and clinically significant ECG results post baseline will be produced showing the worst recorded value post baseline.

8.4.2. Immunogenicity Data

An immune response to a therapeutic drug can lead to generation of anti-drug antibodies within the blood. For the immunogenicity assessment, two types of antibody assays will be performed, a binding anti-drug antibody (ADA) assay and a neutralizing antibody (NAb) assay.

For the binding ADA assay, there will be three testing steps: screening, confirmation and titration. The screening assay produces a result of positive or negative relative to a screening cut point. Positive samples continue with the confirmation assay, which also produces a result of positive or negative relative to a confirmation cut point. For positive confirmation samples, a titre value will also be obtained to quantify the degree of binding in a titration assay. Participants with a positive confirmation result will be positive for the binding ADA assay. Participants who test positive for the binding ADA assay, will be tested for the NAb assay, which also reports results as positive or negative.

Immunogenicity data will be summarised for all subjects in the safety population (excluding data reported during the follow-up period after Week 52), as well as for the subjects entering the follow-up period after Week 52 (using all data). For the binding ADA assay, confirmation results at each visit will be categorised as negative or positive and summarised. NAb assay results will also be summarised.

The highest binding ADA assay confirmatory result obtained for a participant (including any off-treatment data), will be summarised with a positive result being considered higher than a negative one, participants with both positive and negative results being identified in the positive category. Summary statistics for titre results will also be presented. In addition, the highest NAb assay result during the same period will be summarised (again with a positive result being considered higher than a negative one and participants with both positive and negative results will be identified in the positive category).

A summary of treatment emergent positive confirmatory binding ADA assay results in the subset of participants who did not have a positive confirmatory binding ADA assay result prior to the first dose of interventional product will also be presented.

All immunogenicity results (i.e. binding ADA screening and confirmatory assay results, titre values, NAb results and observed mepolizumab concentration) will be listed.

9. PHARMACODYNAMIC ANALYSES

Details of the planned displays are provided in [Appendix 12: List of Data Displays](#) and will be based on GSK Data Standards and statistical principles.

9.1. Pharmacodynamic Analyses

The treatment effect to be estimated (estimand) will be the comparison of mepolizumab 100mg SC to placebo for change from baseline blood eosinophils at Week 52.

9.1.1. Endpoint / Variables

Absolute and ratio to baseline blood eosinophil counts will be summarised at each visit.

9.1.2. Summary Measure

The summary measure of treatment effect will be the ratio of the effect at Week 52 of mepolizumab compared to placebo.

9.1.3. Population of Interest

The population of interest is the Intent to Treat population.

9.1.4. Strategy for Intercurrent (Post-Randomization) Events

Only data collected while the participant was on-treatment will be used in the analysis ('while on-treatment strategy'). Blood eosinophil counts taken more than 28 days following last dose will not be included in the analysis.

Missing data will be assumed to be missing at random.

9.1.5. Statistical Analyses / Methods

9.1.5.1. Statistical Methodology Specification

Endpoint / Variables									

 Ratio to baseline blood eosinophils 									
Model Specification									

 Blood eosinophil counts will be log transformed (\log_e) prior to analysis, transformations for values of 0 GI/L will be based on a value of 0.005 GI/L (see Section 14.6.6). This endpoint will be analyzed using a mixed model repeated measures (MMRM) analysis including the following terms: 
 
 Fixed Categorical:	Treatment group, Region, Visit	
 
 Fixed Continuous:	Baseline \log_e blood eosinophil count,	
 
 Repeated:	Visit	
 
 Interaction Terms:	Visit by baseline, visit by treatment group.	
 
 Participants with missing covariate information will be excluded from the analysis 		Fixed Categorical:	Treatment group, Region, Visit	Fixed Continuous:	Baseline \log_e blood eosinophil count,	Repeated:	Visit	Interaction Terms:	Visit by baseline, visit by treatment group.
Fixed Categorical:	Treatment group, Region, Visit								
Fixed Continuous:	Baseline \log_e blood eosinophil count,								
Repeated:	Visit								
Interaction Terms:	Visit by baseline, visit by treatment group.								

 An unstructured covariance structure for the R matrix will be used by specifying 'type=UN' on the REPEATED line
Model Checking & Diagnostics
The Kenward and Roger method for approximating the denominator degrees of freedom and correcting for bias in the estimated variance-covariance of the fixed effects will be used.
Model Results Presentation

 The estimated means for each treatment group will be calculated from the model using the observed marginal distributions of the sample covariates (OM option in LSMEANS statement). Model-estimates of the absolute mean and mean ratio to baseline will be back-transformed and presented as ratios with corresponding standard errors on the log scale for each treatment group by visit. Estimated treatment differences (Mepolizumab/Placebo) with corresponding 95% CIs and p-values will also be presented.
Subgroup Analyses

 No subgroup analyses are planned for this endpoint
Sensitivity and Supportive Analyses

 No sensitivity/supportive analyses are planned for this endpoint

10. POPULATION PHARMACOKINETIC (POPPK) ANALYSES

The primary goal of this analysis is to characterize the population pharmacokinetics of mepolizumab administered subcutaneously in participants with severe nasal polyps. The influence of subject demographics, baseline characteristics, including disease activity, and co-medication on the pharmacokinetics of mepolizumab in this population will be investigated. The individual subject PK parameters will be estimated and documented for the purposes of any subsequent exposure-response (PK/PD) analyses.

In support of the analysis described below, a dataset will be generated for which specifications will be provided in a separate document.

The details of the planned displays are provided in [Appendix 12: List of Data Displays](#) and will be based on GSK Data Standards and statistical principles. Refer to Data Display Standards & Handling Conventions (Section [14.5.3 Reporting Standards for Pharmacokinetic Data](#)).

10.1. Primary Pharmacokinetic Analyses

A population PK analysis of sparse concentration data will be performed on the PK population.

For subjects withdrawing prematurely from study treatment, all available data will be included in the analysis.

Based on previous knowledge of mepolizumab 100 mg SC pharmacokinetics, concentrations below the limit of quantification (BLQ) of the assay are not anticipated. Any such results will be treated as missing.

Outlier data will be assessed for plausibility; however, the aim is to use all available data whenever possible. Any decision to exclude data will be fully documented and specified in the clinical study report.

10.2. Population Pharmacokinetic Methodology

Sparse blood sampling is implemented in this study for determination of mepolizumab plasma concentration and subsequent data analysis by population PK methods using the most recent population pharmacokinetics model (meta-analysis PK model of data across indications described in GlaxoSmithKline Document Number [2015N238436_00](#)). Since mepolizumab PK following intravenous administration in NP subjects has already been established, the main objectives of this population PK analysis are:

- To evaluate mepolizumab pharmacokinetics in subjects with NP following the subcutaneous administration of a 100 mg dose every 4 weeks.
- To investigate the impact of covariates of interest in the studied NP population (such as baseline characteristics, co-medication) on specific parameters (e.g. clearance) to identify potential sources of inter-individual variability in these parameters.
- To obtain individual plasma concentration predictions for the timepoints at which PD is measured to allow the conduct of population PKPD analyses if deemed appropriate.

Further details are provided in [Appendix 9: Population Pharmacokinetic \(PopPK\) Analyses](#).

10.3. Exploratory Pharmacokinetic Analyses

Complementing the population-PK analysis, a repeated measures linear mixed-effects model of \log_e -transformed concentration will be used to analyse the sparse (Weeks 4, 52 and 68) data. All data will be analysed on an ITT basis using planned Visit, irrespective of withdrawal. The model will adjust for Region and Visit number and consider the covariates listed above. Selection of covariates will be based on biological plausibility, parsimony and a significance level of 0.05. Forwards and backwards selection criteria may be applied as per the population PK model.

10.3.1. Summary Measure

Log-transformed mepolizumab plasma concentration.

10.3.2. Population of Interest

The population of interest is the PK population.

10.3.3. Statistical Analyses / Methods

Endpoint / Variables									

 Plasma concentration 									
Model Specification									

 Plasma concentration will be log transformed (\log_e) prior to analysis, values BQL will be set to missing. This endpoint will be analyzed using a mixed model repeated measures (MMRM) analysis including the following terms: 
 
 Fixed Categorical:	Region, Visit	
 
 Fixed Continuous:	\log_e bodyweight, \log_e creatinine clearance, \log_e serum albumin	
 
 Repeated:	Visit	
 
 Interaction Terms:	None	
 
 
 Participants with missing covariate information will be excluded from the analysis An unstructured covariance structure for the R matrix will be used by specifying 'type=UN' on the REPEATED line 		Fixed Categorical:	Region, Visit	Fixed Continuous:	\log_e bodyweight, \log_e creatinine clearance, \log_e serum albumin	Repeated:	Visit	Interaction Terms:	None
Fixed Categorical:	Region, Visit								
Fixed Continuous:	\log_e bodyweight, \log_e creatinine clearance, \log_e serum albumin								
Repeated:	Visit								
Interaction Terms:	None								
Model Checking & Diagnostics									
The Kenward and Roger method for approximating the denominator degrees of freedom and correcting for bias in the estimated variance-covariance of the fixed effects will be used.									
Model Results Presentation									

 The estimated means for each visit will be calculated from the model using the observed marginal distributions of the sample covariates (OM option in LSMEANS statement). Model-estimates of the absolute mean and mean ratio to Week 4 (accumulation ratio) will be back-transformed and presented as ratios with corresponding standard errors on the log scale by visit. Estimated exposure ratios with corresponding 95% CIs and p-values will also be presented. Effects of bodyweight, creatinine clearance and serum albumin will be evaluated as ratio to standard values and back-transformed and presented as ratios with corresponding standard errors on the log scale. Estimated exposure ratios with corresponding 95% CIs and p-values will also be presented. 									
Subgroup Analyses									

 No subgroup analyses are planned for this endpoint 									
Sensitivity and Supportive Analyses									

 No sensitivity/supportive analyses are planned for this endpoint 									

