**Table 1 Protocol-Required Safety Laboratory Assessments**

Laboratory Assessments	Parameters			
Hematology	Platelet Count	RBC Indices: MCV MCH		WBC count with Differential: Neutrophils Lymphocytes Monocytes Eosinophils Basophils
	RBC Count			
	Hemoglobin			
	Hematocrit			
Clinical Chemistry 	BUN	Potassium	Aspartate Aminotransferase (AST)/ Serum Glutamic-Oxaloacetic Transaminase (SGOT)	Total and direct bilirubin
	Creatinine	Sodium	Alanine Aminotransferase (ALT)/ Serum Glutamic-Pyruvic Transaminase (SGPT)	Total Protein
	Glucose [nonfasting]	Calcium	Alkaline phosphatase	
Routine Urinalysis	
 
• Specific gravity
 
• pH, glucose, protein, blood, ketones, [bilirubin, urobilinogen, nitrite, leukocyte esterase] by dipstick
 
• Microscopic examination (if blood or protein is abnormal)
 
			

Laboratory Assessments	Parameters
Other Screening Tests	
 
• Follicle-stimulating hormone and estradiol (as needed in women of non-childbearing potential only and if urine positive)
 
• Urine human chorionic gonadotropin (hCG) pregnancy test (as needed for women of childbearing potential)
 
• All study-required laboratory assessments will be performed by a central laboratory. 
 
• Hepatitis B and C testing
 
 
 

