14.7.2. Handling of Missing Data

Element	Reporting Detail
General	
 • Missing data occurs when any requested data is not provided, leading to blank fields on the collection instrument: 
 ○ These data will be indicated using a “blank” in data listings. Where all data for a specific visit are missing the visit will be excluded from the listing. ○ Answers such as “Not applicable” and “Not evaluable” are not considered to be missing data and should be displayed. 
Values reported as ‘BLQ’ are not considered as missing data and are handled as detailed in

Element	Reporting Detail
	Section 14.6.6, these values will be displayed in the listings and included in any summary/analysis outputs.
Outliers	
 All data will be included in the summaries and analyses of each endpoint. The exclusion of participants or participant data from any supplementary analyses will be documented within footnotes and where required the clinical study report.
Covariate information	
 Participants with missing information for a covariate included in the analysis model will be excluded from the analysis.

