14.9.2.1. Base Model

In consideration of the sparse sampling (3 samples post-start of treatment over 68 weeks: Week 4, 52 and 68) and the wealth of mepolizumab PK knowledge, the most recent population PK model will be applied directly to the dataset without estimation (e.g. $\text{maxevals}=0$ in NONMEM) and predictions generated, against which the model will be validated prospectively using appropriate goodness of fit tests. For example, the Anderson-Darling and Cramér-von Mises tests are accepted methods of comparing Empirical Distribution Functions for model and data (i.e. PK concentrations) to evaluate whether independent observations (i.e. observed PK concentrations from the study) are adequately described by a model (i.e. most recent population PK model).

The following will be obtained:

- A description of the key models tested during the model development will be provided and tabulated;
- Population mepolizumab plasma PK parameter estimates with 95% CI from the final model will be tabulated. Goodness of fit plots for the final model will be presented;
- Individual post-hoc PK parameter estimates (such as area under the plasma concentration-time curve over the dosing interval $[AUC(0-\tau)]$, $C_{AV} [AUC(0-\tau)/\tau]$) will be summarised descriptively and listed;
- Individual post-hoc predicted plasma concentrations will be summarised descriptively and listed;
- Accumulation ratio estimate will be assessed at Week 52.

The most recent model consists of a two-compartment pharmacokinetic model with first-order absorption and elimination. Bodyweight is incorporated into the model using allometry with fixed physiological allometric exponents of 0.75 and unity for clearance and volumes, respectively. Albumin and creatinine clearance are also included as covariates of mepolizumab clearance on physiological grounds, however their effects are small and not of clinical relevance. Details of the model can be found in report GlaxoSmithKline Document Number [2015N238436_00](#).

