14.9.2.2. Investigation of Covariates

The impact of the following prospectively selected covariates on mepolizumab exposure (e.g. clearance) will be evaluated using the procedures described in Section 14.9.2.3.

Category	Covariates
Demographics	Weight (included in the structural model), age, race, gender, country
Baseline clinical status	Creatinine clearance, albumin (both already included in the current model), serum creatinine, alanine aminotransferase, aspartate aminotransferase, alkaline phosphatase, bilirubin, total protein
Baseline disease status	Total endoscopic NP score (centrally read), mean nasal obstruction VAS, number of previous surgeries, blood eosinophils and baseline OCS dose
Concomitant medications	If data permits ^[1] , e.g. leukotriene receptor antagonists, proton pump inhibitors, statins, antihistamines, pain relief (e.g. paracetamol, NSAIDs) and antihypertensive drugs
Others	Presence/absence of anti-drug antibodies and previous biologics use (monoclonal antibodies).

[1] Attempt to investigate those classes of drug will be made providing data permits.

Covariate selection will be based on physiological plausibility, supported by graphical evaluation (PK parameters vs. covariates), and formally by automated linear model fitting using proc glmselect in SAS 9.4 (or higher). Individual PK parameters and covariates will be log-transformed and standardized before analysis. For forward and backward selections, significance levels of 0.1 and 0.05 will be applied respectively, in line with criteria used in previous analyses. Co-linearity between covariates will be carefully considered.

Identified covariates will then be subjected to traditional covariate analysis (with estimation step) and will follow the procedures described in Section 14.9.2.3. If deemed appropriate box plots of systemic clearance versus covariates of interest (e.g. immunogenicity status) will be provided.

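### Serum albumin is a required covariate in the PK models but has no documented measurement, so on the documented panel the exploratory concentration model in SAP 10.3.3 has no analysable participants

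*SAP*

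**What the plan says.** SAP 10.3.3 specifies a repeated-measures model for log concentration at Weeks 4, 52 and 68. Region and visit are categorical terms; log bodyweight, log creatinine clearance and log serum albumin are continuous terms. The outputs include an albumin effect: "Effects of bodyweight, creatinine clearance and serum albumin will be evaluated as ratio to standard values", with confidence intervals and p-values. On missing covariates the section says: "Participants with missing covariate information will be excluded from the analysis". SAP 14.7.2 states the same rule generally: "Participants with missing information for a covariate included in the analysis model will be excluded from the analysis". No sensitivity or supportive analysis is planned for this endpoint.

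The parent section, SAP 10.3, reads differently. It says the model will adjust for region and visit and will consider other covariates, chosen on plausibility, parsimony and a 0.05 significance level.

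The population PK model also uses albumin. SAP 14.9.2.1 applies an existing model to the data without estimation and says of it: "Albumin and creatinine clearance are also included as covariates of mepolizumab clearance on physiological grounds". The covariate table in SAP 14.9.2.2 repeats this under baseline clinical status ("Creatinine clearance, albumin (both already included in the current model") and names total protein as a separate candidate.

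On the collection side, Protocol 9.4.4 points to Appendix 2 for the tests to be done. The table there is headed "Table 1 Protocol-Required Safety Laboratory Assessments".

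**The concern.** The models need a laboratory value that the protocol does not document collecting. In most models a missing covariate costs a few participants. Here the covariate has no planned source for anyone, and the stated rule is exclusion without imputation. Followed as written, the 10.3.3 model cannot be fitted, and every output from it goes: visit means, ratios to Week 4, and the bodyweight and creatinine-clearance ratios as well as the albumin ratio.

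In the population PK model the gap is milder. The model has an albumin input, no source is documented for it, and the sections give no rule for filling it in.

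If this is not settled beforehand, someone has to decide after unblinding which term to drop or which value to assume. That is avoidable.

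**Working it through.** The plan gives no analysable sample size for this model, so there is no figure to reproduce. The check sets the model terms beside the documented data sources and then applies the exclusion rule.

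**Step 1: what is collected.** Table 1 in Protocol Appendix 2 has 11 chemistry entries: BUN, creatinine, glucose, potassium, sodium, calcium, AST, ALT, alkaline phosphatase, total and direct bilirubin, and total protein. Albumin is not among them, nor is it in the haematology, urinalysis or other screening rows. The schedule of activities adds no albumin test, and neither do the liver-event follow-up assessments in Protocol Appendix 7. The nearest mention is hypoalbuminaemia in the liver-disease exclusion notes (Protocol 6.2, criterion 30), which schedules no test.

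**Step 2: model terms against sources.**

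| Continuous term in SAP 10.3.3 | Documented source |
|---|---|
| Log bodyweight | Physical examination at Visit 1 |
| Log creatinine clearance | Derivable from Table 1 creatinine with weight, age and sex |
| Log serum albumin | None |

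**Step 3: apply the exclusion rule.**

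Analysable n = PK population × share of participants with all covariates present.

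The PK population is ITT participants with a measurable PK sample (SAP section 4). I assume this is at most the planned mepolizumab arm, 200, and that bodyweight and creatinine clearance are complete. The 5% and 10% shares are illustrative assumptions.

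| Albumin available in | Analysable n |
|---|---|
| 0% (documented panel) | 200 × 0 = 0 |
| 5%, through ad hoc tests | 200 × 0.05 = 10 |
| 10%, through ad hoc tests | 200 × 0.10 = 20 |
| 100%, or albumin term removed | 200 × 1 = up to 200 |

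**Step 4: what depends on this model alone.** SAP 14.9.2.1 separately plans a Week 52 accumulation ratio from the population PK analysis, and the display list gives it its own entry (Table 4.7). Cav in SAP 12.2 is 100 mg divided by post-hoc individual clearance times 28 days. That clearance comes from the population PK model and can be obtained with albumin held at a reference value. The PopPK display list has no table or figure titled for the 10.3.3 model. What depends on that model alone is therefore its own visit and covariate ratios.

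**The case against.** The strongest reply is that a missing line in one table does not prove a missing measurement. The table covers required safety tests. SAP 14.8.1 sets concern limits for phosphorus, which is outside Table 1, so the laboratory may have reported more than the protocol lists. (Creatine phosphokinase also appears there, but the liver follow-up list accounts for it.) Appendix 2 allows extra tests, and the PK dataset specifications are separate documents not available here. This stands as a limit on certainty: a reader might infer that every participant certainly lacks albumin, and the documents do not establish that. They show that no source is documented. Ad hoc testing would not rescue the model, as the 5% and 10% rows show.

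A second reply is that SAP 10.3 lets covariates be selected, so an unavailable one need not enter. That too has force, but 10.3.3 then lists albumin among the included terms and requires its effect ratio. The two sections conflict, and the SAP does not say which governs.

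Third, the analysis is exploratory, and SAP 14.9.2.1 itself describes the albumin and creatinine-clearance effects as minor and clinically unimportant. True, and it bounds the harm. It also means there is little reason to let this term empty the model.

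A reader might go further and conclude that the study loses its accumulation ratio, that Cav cannot be computed, or that the population PK analysis also has no participants. The documents do not support this. The first two remain obtainable as shown above. The population PK sections do not themselves state the exclusion rule; although 14.7.2 could be read to reach them, SAP 10.1, in discussing outliers, says the aim is to use all available data where possible.

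**Conclusion.** The point holds in a limited form. Serum albumin is a fixed term and a required output in SAP 10.3.3 and a clearance covariate in the population PK model, with no documented measurement. On the documented panel and under the stated rule, the 10.3.3 model has 0 analysable participants out of up to about 200. This rests on three assumptions: Table 1, the schedule and the liver list are complete for albumin; the fixed list in 10.3.3 governs over the selection wording in 10.3; and the PK population is at most the planned mepolizumab arm.

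The consequence is confined to exploratory PK. The co-primary and secondary endpoints, type I error and safety conclusions do not depend on it.

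**What to change.** Do this before unblinding, in order.

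1. Ask the central laboratory whether albumin was reported. If it was, cite the source and visits in SAP 10.3.3, 14.9.2.1 and 14.9.2.2, and keep the term. Deleting it first would risk discarding a covariate of the model that 14.9.2.1 sets out to validate.
2. If it was not, remove log serum albumin from the terms and effect ratios in 10.3.3, keeping bodyweight and creatinine clearance. In 14.9.2.1 and 14.9.2.2, state that albumin is set to the earlier model's reference value for all participants and is not a tested covariate.
3. In either case, reconcile 10.3 with 10.3.3 so that the covariates are either fixed or selected.

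Total protein should not be swapped in for albumin: 14.9.2.2 already treats it as a separate candidate, and nothing in the documents supports it as a substitute. Adding albumin to samples still to be drawn would not by itself recover baseline values for participants already enrolled.

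The cost is SAP wording. If albumin was not measured, no study-specific albumin effect is reported.
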